The Health Advocate builds a supportive, coaching relationship with the patient and provides non-clinical support, encouragement, and accountability to maximize engagement. The Health Advocate sends encouraging messages and addresses patients’ non-clinical needs, facilitates patient adherence to care programs, promotes patient program retention and engagement through multiple communication channels, and monitors the patients’ Mobile App behaviors. As a part of these activities, the Health

Advocate directly encourages patients to complete the tasks in their Wellframe care program, including reading their health education and completing their surveys.

The Health Advocate co-manages patients with the clinical team via the Wellframe dashboard. The Health Advocate facilitates triage of clinical needs to clinical staff. As a non-clinician, the Health Advocate operates under the supervision of Wellframe's team of licensed clinicians (physicians and nurse practitioners), and all patient communication adheres to structured protocols and guidelines set forth by Wellframe clinical leadership.

III. RESEARCH DESIGN AND METHODS

Sample size: 150 post-PCI at Massachusetts General Hospital (MGH) and Brigham & Women's Hospital (BWH): 100 with myocardial infarction, 50 with symptomatic coronary artery disease without myocardial infarction

Inclusion/Exclusion Criteria

- Acute myocardial infarction – defined by typical symptoms, characteristic kinetics of cardiac biomarkers or characteristic EKG changes

Or

Symptomatic coronary artery disease without myocardial infarction – defined by typical symptoms (i.e. angina) and signs (i.e. abnormal non-invasive cardiovascular testing: stress testing or coronary CTA)

Inclusion Criteria

- Age 21-85
- English-speaking
- PCI: balloon angioplasty, bare-metal stent, or drug-eluting stent at MGH
- Smartphone or Tablet (iOS or Android)
- Long term provider in Massachusetts (or records available through Care Everywhere)

Exclusion Criteria

- Recent (within 1mo) illicit substance use or alcohol abuse
- In-hospital AMI
- Known pregnancy
- Dementia or cognitive disability
- Incarceration

Study Outcomes

Clinical and Utilization Outcomes

Clinical outcomes will be ascertained from electronic medical records. Patients will also be called at 90 days to determine potential readmission, representation, and cardiac rehabilitation enrollment at other hospitals or clinics during the follow-up period. The following outcomes will be assessed:

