- D.3. Level and method of blinding:** Open-label

- D.4. Randomization time point:** NA

- D.5. Timeframe of all study periods:**

D.5.a. Intervention arm: screening (02/2018-06/2019), baseline (02/2018-06/2019), intervention period (02/2018-09/2019), follow-up (05/2019-09/2019)

D.5.b. Historical control arm: baseline (01/2015-12/2017), follow-up (03/2015-03/2018)

D.6. Inclusion/Exclusion criteria:

D.6.a: Inclusion: 21-85 years old, fluency in English language, underwent PCI at either MGH or BWH during screening period for either symptomatic CAD or ACS, own a smartphone or tablet

D.6.b: Exclusion: Recent (<1mo) drug or alcohol abuse, in hospital AMI, pregnancy, cognitive delay/dementia, incarceration

D.7. Study variables:

Age	Age at time of enrollment into study as coded into Partners EHR
Sex	Gender as coded into Partners EHR
State	State of residence (Massachusetts vs Non-Massachusetts) at time of enrollment into study as coded into Partners EHR
PCI Type	Reason for percutaneous coronary intervention (PCI). Myocardial infarction (MI) coded as chart diagnosis of MI or positive serologic (troponin) values prior to PCI. All other PCI without evidence of myocardial necrosis coded as elective.
Partners PCP	Coded "yes" for patients with PCP in Partners EMR working primarily for Partners Healthcare system. Coded "no" for patients with PCP in Partners EMR not within Partners system or missing PCP data.
Insurance Type	Coded based on primary insurance listed in Partners EMR.
Site	Coded based on location of incident PCI procedure (either Massachusetts General Hospital [MGH] or Brigham and Womens Hospital [BWH])
Hypertension	Chart diagnosis of HTN prior to or at time of incident PCI
Hyperlipidemia	Chart diagnosis of HLD prior to or at time of incident PCI, LDL-C >129 at time of incident PCI or Triglycerides >150 at time of incident PCI
Type 2 Diabetes	Chart diagnosis of DM2 prior to or at time of incident PCI, or Hemoglobin A1c > 6.4 at time of incident PCI
Peripheral Arterial Disease	Chart diagnosis of PAD prior to or at time of incident PCI or history of peripheral arterial intervention
Smoking	Chart history of smoking (codified as current smoker, former smoker (quit >1 month prior to PCI), or never smoker). For analysis, variable was condensed into never smoker or ever smoker (either current or former).
Coronary Artery Disease	Chart diagnosis of CAD prior to or at time of incident PCI or history of CABG or prior PCI

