30-day Content Completion	Percentage of content tasks (articles opened) completed within 30 days on app
90-day Content Completion	Percentage of content tasks (articles opened) completed within 90 days on app
30-day Survey Completion	Percentage of survey tasks completed within 30 days on app
90-day Survey Completion	Percentage of survey tasks completed within 90 days on app
30-day Weekly Patient Engagement	Percentage of days in which patient completed at least one task from the app checklist (survey, article, physical activity goal, encouragement) or sent a message to clinical team at least once over the previous 7 days within 30 days on app.
90-day Weekly Patient Engagement	Percentage of days in which patient completed at least one task from the app checklist (survey, article, physical activity goal, encouragement) or sent a message to clinical team at least once over the previous 7 days within 90 days on app.
30-day Daily Patient Engagement	Percentage of days in which patient completed at least one task from the app checklist (survey, article, physical activity goal, encouragement) or sent a message to clinical team within 30 days on app.

90-day Daily Patient Engagement	Percentage of days in which patient completed at least one task from the app checklist (survey, article, physical activity goal, encouragement) or sent a message to clinical team within 90 days on app.
Patient Satisfaction	Average patient response on app satisfaction via app survey function.
Patient Messages Sent	Number of total messages sent by patient within 90 days on app
Patient Messages Received	Number of total messages sent to patient within 90 days on app
Patient Messages Opened	Percentage of messages sent to patient that were opened
Patient Message Response	Percentage of messages sent to patient with at least one message response from patient
Patient Physical Activity	Percentage of days where patient met physical activity goal (default of 500 steps) within 90 days on app.
Days to First Message	Days until first message sent from care team to patient
Clinical Messages	Percentage of patients receiving at least one message from app care team within 90 days on app.

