D.8. Sample size and power: We have at least 95 percent power with 150 enrolled participants, 450 matched historical controls, with alpha equal to 0.05, to detect an effect of at least 2-fold increase in the primary clinical outcome, likelihood of enrollment in cardiac rehabilitation within the 90 day study period with baseline 25% enrollment rates⁶.

E. General Considerations:

E.1. Analysis populations:

E.1.a.: Full analysis population: All intervention subjects who downloaded the study application and 3:1 matched historical controls.

E.1.b.: Engagement population: All intervention subjects who downloaded the study application.

E.2. Covariates and subgroups: Sex (M/F), State (MA/non-MA), PCI Type (MI/Elective), DM2 (Y/N), Partners PCP (Y/N), Insurance Type (Commercial/Medicaid/Medicare/Other)

E.3. Missing data: Missing data values for participants who fit inclusion criteria will default to zero or “no” for dichotomous variables. Missing data values for participants will default to “unknown” or “other” for continuous or categorical variables.

F. Summary of study data: All continuous variables will be summarized using the following descriptive statistics: n (non-missing sample size), mean, standard deviation, median, maximum and minimum. The frequency and percentages (based on the non-missing sample size) of observed levels will be reported for all categorical measures. In general, all data will be listed, sorted by site, treatment and subject, and when appropriate by visit number within subject. All summary tables will be structured with a column for each treatment in the order (Control, Experimental) and will be annotated with the total population size relevant to that table/treatment, including any missing observations.

G. Protocol deviations: Subjects who do not fit inclusion criteria will be removed from the data set prior to analysis. Subjects with missing data will be treated as discussed above (Section E.3.)

H. Efficacy Analyses: The Cox Proportional Hazards model will be used to assess efficacy of the intervention (use of the application) on the primary outcome. The percentage of subjects attending cardiac rehabilitation enrollment within 90 days of discharge from incident PCI hospitalization will be compared across groups. A secondary analysis between the two groups will be conducted adjusting for covariates such as age, sex, insurance type, state, diabetes, and partners PCP).

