Primary analysis will verify balance in matching (unadjusted) via Chi-squared model for binary variables and ANOVA for categorical variables

I. Engagement Analyses: Overall engagement by patients in the intervention arm with the Wellframe application will be assessed by evaluating the number of days or weeks with at least one task completed (including surveys done, content read, activity goals reached and medication reminders used) within both a 30- and 90-day period. Individual task completion rates will also be assessed and reported within 30- and 90-day periods. Use of messaging between patients and health advocates will also be assessed during a 30- and 90-day period. Changes in these metrics across 30- to 90-days will be evaluated.

J. Exploratory Analyses:

We will compare subgroups (MI/elective) using linear regression across the 30-day engagement metrics above to evaluate predictors of engagement (adjusting for both 30-day engagement as well as matching covariates such as age, sex, PCI type, state, insurance, partners PCP and site).

We will use the Cox Proportional Hazards model to assess efficacy of the intervention on lowering rate of ER visits for cardiovascular reasons, ER visits for all causes and hospitalizations for all reasons.

We will use the Cox Proportional Hazards model to assess efficacy of the intervention on reducing rates of repeat PCI, stroke, non-fatal MI, cardiovascular cause of death and all cause death within 90 days of enrollment.

We will use the Cox Proportional Hazards model to assess for improvement in percentage of patients adhering to cardiovascular follow up appointments within 30 days of discharge.

K. Type I Error Control: We will control for error by limiting our primary outcome to 90-day cardiac rehabilitation enrollment. All subsequent analysis, including secondary outcomes, will be considered exploratory.

L. References:

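### SAP Section J adjusts the MI/elective comparison of 30-day engagement for 30-day engagement itself, and lists the exposure again among the adjusters

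*SAP*

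**What the plan says.** Section J of the SAP (Exploratory Analyses) gives the model in one sentence. Exposure and outcome: "We will compare subgroups (MI/elective) using linear regression across the 30-day engagement metrics above to evaluate predictors of engagement". Adjusters: "adjusting for both 30-day engagement as well as matching covariates such as age, sex, PCI type, state, insurance, partners PCP and site".

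Three definitions bear on it.

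- **PCI type (D.7)** has two levels. After MI is defined, "All other PCI without evidence of myocardial necrosis coded as elective". It is the same variable as the MI/elective contrast.
- **Engagement metrics (D.7).** Weekly and daily engagement are built from the same events, a checklist task completed or a message sent. The weekly definition ends "or sent a message to clinical team at least once over the previous 7 days within 30 days on app" and the daily one "or sent a message to clinical team within 30 days on app".
- **Population (E.1.b):** "Engagement population: All intervention subjects who downloaded the study application". The protocol's target mix (Section III, sample size) is "100 with myocardial infarction, 50 with symptomatic coronary artery disease without myocardial infarction".

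Two other places address the same question. Table 4.3, a Pearson correlation analysis, lists MI/elective once among baseline factors and has no engagement metric as a predictor. Figure 8 shows the same kind of correlation matrix with MI as one factor. Section K makes everything other than the primary outcome exploratory.

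**The concern.** The question is whether MI and elective patients use the app differently in the first 30 days. Adjusting for 30-day engagement holds fixed the quantity whose difference is to be estimated. What remains is the part of one engagement metric that another does not explain, which is not the MI/elective difference.

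The words "such as" in the sentence leave the list of matching covariates open, but 30-day engagement stands outside that list as a firm adjuster. An analyst who follows the text would include it.

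Listing PCI type again is the lesser fault. Two copies of one variable cannot both be estimated, so software drops one and the fit is otherwise unchanged.

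At stake is the interpretation of the only regression the SAP plans of engagement on patient type.

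**Working it through.** The documents give no figure for this analysis, so there is nothing to reproduce. The check is algebra with assumed inputs.

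**Inputs.** From the protocol: 100 MI and 50 elective patients. Assumed: a within-group SD of 25 percentage points for each metric, a true MI-elective difference in the outcome (dY) of 10 points, a difference in the adjusting metric (dX) of 5, 10 or 15 points, and a within-group correlation (rho) between the two of 0.5, 0.8 or 0.9. The baseline covariates are left out of the closed form.

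**1. PCI type entered twice.** A design matrix with intercept, MI, age and MI again has rank 3 with 4 columns. One MI term is dropped; no other harm follows.

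**2. Same metric on both sides.** The metric predicts itself with slope 1, so the MI coefficient is dY - 1 x dY = 0 and R-squared is 1.

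**3. A different 30-day metric as adjuster.** With one binary exposure and one continuous adjuster, the MI coefficient is dY - b x dX, where b is the within-group slope. At equal SDs b = rho, so

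coefficient = dY - rho x dX.

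The residual SD is 25 x sqrt(1 - rho²), and the standard error is approximately the residual SD x sqrt(1/100 + 1/50). Power is two-sided at 0.05.

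Unadjusted: SE = 25 x sqrt(0.03) = 4.33; 10/4.33 = 2.31; power 63%.

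Adjusted, dY = 10:

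| dX | rho 0.5 | rho 0.8 | rho 0.9 |
|---|---|---|---|
| 5 | 7.5 (51%) | 6.0 (63%) | 5.5 (about 82%) |
| 10 | 5.0 (26%) | 2.0 (12%) | 1.0 (8%) |
| 15 | 2.5 | -2.0 | -3.5 |

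Cells give the coefficient in points, with power in brackets for the first two rows. For example, at dX 10 and rho 0.8 the coefficient is 10 - 0.8 x 10 = 2.0, SE = 15 x 0.1732 = 2.60, ratio 0.77, power 12%. At dX 5 and rho 0.8 it is 6.0/2.60 = 2.31, the same ratio as unadjusted.

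No cell returns the 10 points that separate the groups. Power falls in some cells, is unchanged in one, and rises in another because the residual SD shrinks too.

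**4. Is a rho in this range plausible?** By definition a day with daily engagement is also a day with weekly engagement, so the two metrics overlap. Patient-days simulated under the D.7 definitions, with six assumed engagement patterns, gave rho from 0.68 to 0.83. A 10-point daily difference became 3.3 to 5.4 points after adjustment for weekly engagement. The exact size depends on the pattern assumed, particularly on how patients who stop using the app are modelled.

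**The case against.** **The association is already planned without the fault.** Table 4.3 and Figure 8 correlate daily and weekly engagement with baseline factors, including MI/elective, and use no engagement metric as a predictor. This stands, and it limits the impact to the adjusted regression. It also suggests that the adjuster in Section J is a drafting slip. It does not repair Section J, which promises a covariate-adjusted comparison that a correlation matrix cannot supply.

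**An analyst would notice.** A zero coefficient with R-squared 1 would be caught at once. That is true of the same-metric case only; adjusting one engagement metric for another yields an ordinary-looking result.

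**A 90-day outcome may have been meant.** The sentence says 30-day. D.7's 90-day daily metric, "or sent a message to clinical team within 90 days on app", also includes the first 30 days, so this intention would have to be written out before it could be assessed.

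**The numbers could be read too strongly.** A reader might infer from the table that the adjustment always costs power, or that it will reverse the sign or create a difference where none exists. The documents support none of these as a general result. Power can rise, as at dX 5 and rho 0.9. Sign reversal in the table needs a larger difference in the adjuster than in the outcome. A spurious difference needs a metric with no MI/elective difference beside an overlapping one with a large difference. In the simulated patterns, a 10-point daily difference always came with a weekly difference of 3.6 to 9.4 points.

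**Conclusion.** The concern holds as a specification error in one exploratory regression. As written, Section J gives an MI/elective coefficient of exactly 0 if the same metric is on both sides. With another 30-day metric as adjuster, the coefficient is dY - rho x dX at equal SDs: 5.0, 2.0 or 1.0 points instead of 10 in the equal-difference example. The zero needs no assumption. The other sizes rest on the assumed SD, differences and correlations and on the 100/50 target mix. The repeated PCI type is redundant only.

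A reader might infer that the efficacy results are affected. They are not: the 90-day cardiac rehabilitation outcome does not pass through this regression, and Section K makes Section J exploratory.

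One editorial mismatch is nearby. Models 2 and 3 in the output shells for the primary outcomes are labelled as including the matching criteria, but the rows list six of the eight factors in D.2.b. PCI type and site are missing, as they are from the list in Section H. A reader might infer confounding from this. Since controls are matched on both factors, the documents support only a wrong label.

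**What to change.** Replace the Section J sentence with wording to this effect: *In the engagement population, each 30-day engagement metric will be regressed on PCI type (MI/elective), adjusting for age, sex, state, insurance type, Partners PCP and site; no engagement metric is an adjuster.* DM2 is the one D.2.b matching factor that Section J does not name. Adding it would complete the set, and the revision should say that it has been added.

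Editorial only: either relabel models 2 and 3 so that they do not claim all matching criteria, or add PCI type and site consistently in Section H and in the shells.

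The cost is SAP wording and a few lines of code, since every variable named is already in D.7. No new data are needed. The SAP is dated 12/28/19 and D.5.a ends intervention follow-up in 09/2019, so the change comes after follow-up and should be dated, with the reason stated.

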PRINCIPAL/OVERALL INVESTIGATOR

[name]

PROTOCOL TITLE

A smartphone-based application post-myocardial infarction to manage cardiovascular disease risk

FUNDING

Boston Scientific

VERSION DATE

02/26/2019

I. SPECIFIC AIMS

Specific Aim 1: To recruit and onboard 100 patients sustaining a myocardial infarction and 50 patients with symptomatic coronary artery disease without myocardial infarction who have undergone PCI with the Wellframe patient engagement platform. Patients will be recruited during index cardiac hospitalization in the inpatient setting.

Specific Aim 2: To determine feasibility of inpatient onboarding of the Wellframe patient engagement platform in the setting of acute myocardial infarction. We will evaluate process outcomes, including proportion of eligible participants agreeing to participate, survey completion rates, content engagement, patient application engagement, and patient satisfaction scores.

Specific Aim 3: To assess the clinical efficacy of the Wellframe patient engagement platform post-myocardial infarction compared to matched historical controls. We will also evaluate outpatient clinic follow-up rates after hospitalization as well as cardiac rehabilitation enrollment rates (primary outcome) for all participants. We will evaluate 90-day and 30-day readmission and ED visit rates for post-myocardial infarction participants.

We hypothesize that the patient engagement platform will be an efficient method for cardiology staff to engage, follow-up, and educate patients peri-percutaneous coronary intervention (PCI) in the setting of acute myocardial infarction.

II. BACKGROUND AND SIGNIFICANCE

Public Health Significance

Myocardial infarction is a leading cause of morbidity and mortality in the United States and worldwide.^{1,2} Acute management of myocardial infarction involves pharmacological and revascularization strategies to reduce recurrent ischemic events, including cardiovascular death.^{3,4} Secondary prevention measures include adherence to guideline-based pharmacologic strategies, management of cardiovascular risk factors, diet and lifestyle counseling, and participation in cardiac rehabilitation. Both patient- and treatment-specific factors are associated with short-term adverse events.

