- Utilization and Attendance
 - 4 Week Follow-up Appointment: % of patients who attend cardiology follow-up appointments after PCI
- **Readmission Rates**
 - **30 Days- Primary Outcome**
 - 60 Days
 - **90 Days – Secondary Outcome**
- Representation Rates (ED presentation with hospitalization)
 - 30 Days
 - 60 Days
 - 90 Days
- **Enrollment in clinic-based cardiac rehab**
 - **% of patients discharged after intervention who attend at least one session of clinic-based cardiac rehab -Secondary Outcome**
- Cost Effectiveness

[figure not shown]
Process Outcomes

These data will be provided by Wellframe to the PI. “Conversion rate” will be the primary outcome as this will indicate patient acceptability of initiating the platform and the remainder listed below will be secondary outcomes. The proportion of individuals with cardiovascular disease who accept a smartphone application upon discharge is largely an outstanding question. We hypothesize that >50% of eligible and recruited patients will enroll in the Wellframe app. Data from Wellframe will be used to assess:

- Conversion Rate: Number of patients who enroll in Wellframe app out of the number of patients eligible for participation
- Medication Adherence: % of medication reminder tasks that were completed
- Content Completion: % of content tasks that were completed
- Survey Completion: % of survey tasks that were completed
- Patient Engagement:
 - % Weekly engagement (percent of days in which patient had engaged at least once over the previous 7 days)
 - % Daily engagement (percent of days in which patient had engaged)
- Patient Messaging:
 - Number of messages sent
 - Percent of messages sent to patients that were opened at any point
 - Percent of messages sent to patients that had at least one message from the patient afterwards
- Patient Satisfaction: average response to patient satisfaction questions asked through app’s survey functionality
- Patient Physical Activity
- Clinical Messaging:
 - Total number of messages sent
 - Percent of patients who received at least one message

Primary and secondary outcomes are labeled and in bold, all other outcomes are exploratory outcomes.

Schema

■ Subject Enrollment

■ Study Procedures

■ Study Closeout and Post Study Follow-up

Subject Enrollment

Overview

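### The protocol names two different primary efficacy outcomes, and the SAP, dated after follow-up ended, keeps one without comment, so these documents do not show that section K's single primary was fixed in advance

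*SAP*

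**What the plan says.** Protocol, version 02/26/2019:

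- Section I, Specific Aim 3 names "cardiac rehabilitation enrollment rates (primary outcome) for all participants". The same aim looks at readmission and ED visits only in participants with myocardial infarction (planned n = 100).
- Section III, Clinical and Utilization Outcomes, marks readmission at "30 Days- Primary Outcome" and at "90 Days – Secondary Outcome". Rehabilitation is the percentage "of patients discharged after intervention who attend at least one session of clinic-based cardiac rehab -Secondary Outcome". The cardiology appointment ("4 Week Follow-up Appointment: % of patients who attend cardiology follow-up appointments after PCI") carries no rank.
- Section III, end of Process Outcomes, gives the rule for reading the list: "Primary and secondary outcomes are labeled and in bold, all other outcomes are exploratory outcomes". Conversion rate is named separately: it "will be the primary outcome as this will indicate patient acceptability of initiating the platform".
- Section VII powers 30-day readmission as the primary clinical outcome: 150 participants, 600 controls, alpha 0.05, a 2.5-fold effect, a 5% rate, and power of at least 80%.

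SAP, version 12/28/19:

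- C.1 makes 90-day rehabilitation enrolment primary, and C.2 makes 30-day cardiology follow-up secondary.
- D.3 states that the study is open-label. D.5 starts enrolment in 02/2018 and ends follow-up in 09/2019 for the app group and 03/2018 for the controls.
- D.8 powers rehabilitation: 150 against 450 controls, 25% baseline, a 2-fold increase, and power of at least 95%.
- Section K says "We will control for error by limiting our primary outcome to 90-day cardiac rehabilitation enrollment" and makes everything else exploratory. Section J and the table shells place hospitalisation and readmission among the exploratory analyses.
- D.7 counts the 90 days to the rehabilitation intake session from the PCI. Section H counts them from discharge.

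**The concern.** The documents give two answers to the question of which result decides efficacy. Under the SAP it is rehabilitation enrolment. Under the protocol's outcome list and power section it is 30-day readmission. If the two results disagree, the trial is positive under one text and not under the other.

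Section K's only protection is that there is a single primary. That protects the 5% level only if the outcome was fixed without regard to results. The SAP version carrying the statement is dated after follow-up, the study is open-label, and outcomes come largely from records that staff could consult. The SAP does not say that the protocol also named readmission, that its power section was replaced, or why. A reader of the SAP alone would not learn that a choice had been made.

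The two start points for the 90 days add a smaller ambiguity: even the retained primary is not one fully specified outcome.

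**Working it through.** **1. Labels side by side**

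| Outcome | Protocol Aim 3 | Protocol outcome list | Protocol VII | SAP |
|---|---|---|---|---|
| Rehabilitation enrolment | primary | secondary | not powered | sole primary (C.1, D.8, K) |
| 30-day readmission | evaluated, MI participants only | primary | primary, all 150 | exploratory (J, K, table shells) |

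The conflict lies inside one protocol version. Conversion rate is a process primary and does not explain it.

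**2. Dates**

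Enrolment began 02/2018. The protocol version is dated 02/26/2019, about a year later. Follow-up ended 09/2019. The SAP version is dated 12/28/19, about three months after that. Aim 3 therefore named rehabilitation before follow-up ended, but neither protocol label is shown to predate all outcome data.

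**3. The plan's own power figures**

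Two-sided alpha 0.05, normal approximation with pooled null variance, matching ignored:

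power = Φ[(|p1 − p2| − 1.96·s0) / s1], where s0² = p̄(1 − p̄)(1/n1 + 1/n2) and s1² = p1(1 − p1)/n1 + p2(1 − p2)/n2.

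SAP D.8, 150 against 450, 50% against 25%: p̄ = 0.3125, s0 = 0.0437, s1 = 0.0456, so (0.25 − 1.96 × 0.0437)/0.0456 ≈ 3.60 and power is 99.98%. The stated 95% is met. If 2-fold means a hazard ratio (1 − 0.75² = 43.75%), power is about 98% to 99%. If it means an odds ratio (40%), power is 93%.

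Protocol VII does not say which group has the 5% rate or which way 2.5-fold runs, so each reading is shown:

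| App group vs controls | 150 vs 600 | 150 vs 450 (SAP number) |
|---|---|---|
| 5% vs 12.5% | 80% | 78% |
| 12.5% vs 5% | 86% | 84% |
| 2% vs 5% | 32% | 32% |

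Each document's power claim can be reproduced on some reading, but they concern different outcomes, effects and control numbers, so neither can stand in for the other.

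**4. The readmission population**

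If Aim 3's restriction to MI participants applies, n is 100. Assuming the same 4:1 ratio (100 against 400), the three rows become 59%, 73% and 20%. The protocol's 80% therefore holds only for all 150.

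**5. What section K protects**

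One outcome fixed in advance gives 5% two-sided, or 2.5% for a false claim of benefit. Suppose instead that either of two null outcomes could be taken as primary after both results were seen. The chance of at least one nominal rejection is 1 − 0.95² = 9.75% two-sided if the tests are independent, and 1 − 0.975² = 4.9% for false benefit. With bivariate normal test statistics:

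| Correlation | Two-sided | False benefit |
|---|---|---|
| 0 | 9.75% | 4.9% |
| 0.3 | 9.5% | 4.8% |
| 0.5 | 9.1% | 4.5% |
| 0.8 | 7.8% | 3.9% |

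The correlations are assumptions, since the documents give none.

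**The case against.** The best defence is that rehabilitation was not invented late. Aim 3 called it primary in a protocol dated seven months before the end of follow-up, and measured against Aim 3 the primary did not move at all. This stands, and it rules out a stronger reading that the sequence of dates invites: that the sponsor switched the primary after seeing the data. Nothing in the documents shows that. A version date is not the date of a decision, and earlier versions of either document may exist.

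A reader might also infer that the SAP reshuffled every ranked outcome. That holds only against the outcome list. For cardiology follow-up it is weak even there: C.2 calls it secondary, but section J and the table shells treat it as exploratory, and section K gives secondary outcomes no confirmatory role. The change that matters is rehabilitation against 30-day readmission.

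It is tempting, too, to say that a rehabilitation gain with no readmission difference is the likely result because readmission power is only 32%. That figure belongs to one reading (5% falling to 2%). Another benefit reading, 12.5% falling to 5%, gives 80%.

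Finally, section K's logic is sound if the choice was fixed without regard to results, and the readmission analyses are still planned. Both points stand. What they leave open is that Aim 3 is contradicted by two other places in the same version, so it cannot by itself establish pre-specification.

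**Conclusion.** The concern holds in this form. The protocol conflicts with itself on the primary efficacy outcome. The SAP settles the conflict after follow-up without saying so, and these documents do not show when or why rehabilitation was fixed or what outcome data had been seen. Section K's 5% is therefore conditional on something not documented here.

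The size is a conditional upper figure: 7.8% to 9.75% two-sided instead of 5%, assuming a free choice between the two outcomes after both results were known and correlation between 0.8 and 0. If the choice was fixed without regard to results, there is no inflation from this source. Bias from the non-randomised historical comparison is separate and not counted, so a nominal 5% does not guarantee a true 5% either way.

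Two further conflicts belong to the same reconciliation: the start of the 90-day rehabilitation window (PCI or discharge), and the readmission population (100 MI participants or all 150). The point should be settled before any efficacy claim is made. It is not evidence of misconduct or of a result-driven switch.

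**What to change.** 1. By a dated amendment, or a changes-from-protocol entry in the SAP, bring Protocol Aim 3, the protocol outcome list, Protocol VII and SAP C.1, D.8 and K to one primary efficacy outcome. Give it one matching power statement that names the effect measure and the number of controls. Record that the outcome list and Protocol VII had 30-day readmission as primary.
2. Use one rehabilitation definition throughout, with one start for the 90 days. The D.7 definition is one that Partners records can supply for both groups.
3. In section K, state when and why rehabilitation was fixed and what participant and control outcome data had been seen by then. A late amendment cannot supply this; only documentation of timing and data access can. If there is none, drop the Type I error control claim and describe the rehabilitation result as not shown to be pre-specified.
4. Report the already planned 30-day readmission estimate with its confidence interval. Identify it as the outcome the protocol list labelled primary and Protocol VII powered, and settle whether it covers MI participants only or everyone.

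The cost is wording and reporting only, with no new data. The one substantive consequence is a weaker efficacy claim if the timing cannot be documented.
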